9 RESEARCH METHODS

The research methods described here have been endorsed by European Medicines Agency (EMA) Pharmacovigilance Risk Assessment Committee in several protocols available at the European Network of Centres for Pharmacoepidemiology and Pharmacovigilance (ENCePP) website.¹⁴

9.1 STUDY DESIGN

This will be a national, multicentre, prospective, cross-sectional, and multi-channel survey based on primary data collection, conducted separately among qualified HCPs (physicians, nurses and pharmacists) and STAMARIL® vaccinees (or their parents/guardians if vaccinees are younger than 18 years old) in the UK (England, Wales, Northern Ireland and Scotland).

The survey will be conducted primarily through a web questionnaire. Also, a paper version of the questionnaire will be offered to vaccinees only.

9.2 SETTING

The survey will be conducted among qualified HCPs from designated authorised YFVCs and yellow fever vaccinees (or their parents/guardians if vaccinees are younger than 18 years old) in the UK.

Based on the NaTHNaC Annual Return 2019 report,¹³ there were a total of 2,821 YFVCs that were designated in 2019 in England, Wales, and Northern Ireland, and 168 YFVCs in January 2021 in Scotland based on Scotland's NHS website. Based on the NaTHNaC Annual Return 2020¹³ report, there were a total of 2,295 YFVCs that remained designated in 2020 in England, Wales, and Northern Ireland. In addition, 123 YFVCs remained designated in Scotland as of January 2022.¹⁵

9.2.1 Duration of the study

The fieldwork will start after the aRMMs have been implemented to enable the assessment of effectiveness. Generally, a 6 to 12month period is considered after the implementation of the aRMMs to allow for their completion. The survey will be conducted within 12 to 18 months following the distribution of the local aRMMs in the UK as per the European guideline on good pharmacovigilance practices (GVP) – Module XVI (Rev 3).

9.2.2 Eligibility criteria

The target population of the survey will be qualified HCPs (physicians, nurses and pharmacists) and yellow fever vaccinees (or their parents/guardians if vaccinees are younger than 18 years old).

9.2.2.1 Inclusion criteria

The following criteria must be met in order to be enrolled in the study:

1. For HCPs: Qualified HCPs from designated authorised YFVCs who have provided consultation for yellow fever vaccine administration and/or administered yellow fever vaccines in the UK in the past 12 months and are willing to consent to participate in the

Property of the Sanofi Group - strictly confidential

31-May-2023

Version number: 3.0

- survey. A qualified HCP refers to the one who has undertaken the yellow fever training programme, sponsored by the NaTHNaC or PHS during the past 24 months.
- 2. For vaccinees: Individuals who receive yellow fever vaccine in the UK and are willing to consent (or their parents/guardians, if individuals are younger than 18 years old) to participate in the survey.

9.2.2.2 Exclusion criteria

Individuals meeting any of the following criteria are not eligible for participation:

1. For HCPs:

- a. Who declare having conflict of interest with the survey (i.e., HCPs employed by regulatory bodies, or pharmaceutical industries, etc).
- b. Who are unable or not willing to provide voluntary consent to participate in this survey conducted in the UK.
- c. Who are not qualified to provide consultation for yellow fever vaccine administration and/or administer yellow fever vaccines in the UK (i.e., HCPs who have not undertaken yellow fever training sponsored by the NaTHNaC or PHS in the past 24 months).
- 2. For vaccinees (or their parents/guardians if vaccinees are younger than 18 years old):
 - a. Who declare having a conflict of interest with the survey (i.e., employed by regulatory bodies, or pharmaceutical industries etc., or are immediate family of qualified HCP's of designated authorised YFVCs or are employed by YFVCs).
 - b. Who are unable or not willing to provide voluntary consent to participate in this survey conducted in the UK.

9.2.3 Analysis population(s)

All eligible HCPs (physicians, nurses and pharmacists) and vaccinees (or their parents/guardians if vaccinees are younger than 18 years old) who complete the web/paper questionnaires (totally or partially for the paper version) will be included for analysis.

9.2.4 Modalities of recruitment

All YFVCs will be included in the sampling plan so that the results of the survey are representative of all regions in the UK (England, Wales, Northern Ireland and Scotland).

9.2.4.1 HCPs selection

It is expected that nurses will represent the majority of HCPs in the YFVCs. Other HCPs to be included in the study will be general practitioners, and a minority will be pharmacists.¹⁶

The initial identification of participating HCPs will be based on the list of all YFVC practices as reported by the NaTHNaC¹⁷ in each region and HPS¹⁸. The lists of YFVCs will be reconciliated

with OneKey lists (OneKey, IQVIA) in order to retrieve contact details for HCPs working in each YFVC. OneKey is an IQVIA managed database with information of HCPs in each of the relevant specialities in the targeted country. OneKey databases are constructed and updated through manual and automated means from various sources, including publicly available sources. Information collected includes HCP personal information (e.g. age, gender, contact details) and professional information (e.g. year of graduation, specialties, practicing status). These lists are widely used for the recruitment of HCPs in clinical trials, observational studies and surveys.21, ²²

Since the study objective is to determine the extent of HCPs' awareness and knowledge of the safety information in the aRMMs, only HCPs who have provided consultation for yellow fever vaccine administration and/or administered the yellow fever vaccine in the past 12 months will be selected. As this information is not available in the lists of HCPs, the survey will be preceded by a set of questions to check the eligibility of HCPs. Among these, it will be asked if the HCP has provided consultation to yellow fever vaccinees and/or administered the yellow fever vaccine in the past 12 months. If the answer is "no", the survey will not open to that HCP.

According to the Annual Return 2020¹³ report, the number of HCPs administering yellow fever vaccines varied for each YFVC and around 89% of YFVCs had 1 to 3 HCPs administering yellow fever vaccines. Therefore, to limit selection bias, we will recruit a maximum of 3 HCPs per centre. However, in case the target sample size is not achieved, this cap may be lifted to a maximum of 5 HCPs per centre.

HCPs recruitment and survey will be conducted by the following process:

- HCPs will be invited to participate in the survey by email and/or phone. An email
 invitation will include a web link directing to the questionnaire. In the invitation, the
 survey background and objectives, the contact information for questions, and the proposed
 compensation will be explained to the HCPs. Compensation will be compliant with the
 relevant guidelines and the fees will compensate for the actual effort and time needed to
 fill out the questionnaire.
- If the HCPs agree to participate in the survey, they can access the survey and the instructions for the web questionnaire by clicking on the email link.
- If the questionnaire is not completed in the first attempt, HCPs will receive a reminder email (first reminder) 1 week after the initial invitation.
- If the web questionnare remains incomplete, a second reminder will be sent about 2 weeks after the initial invitation.
- If the questionnaire still remains incomplete, a third (and final) reminder will be sent 3 weeks after the initial invitation.

An HCP will be considered unreachable if he/she has been contacted up to 5 times without an answer. For each recruited HCP, the number of times the HCP is contacted, as well as the date and time when he/she completes the web questionnaire, will be recorded. HCP recruitment will be competitive.

Version number: 3.0

31-May-2023

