Furthermore, a patient information leaflet (PIL) should be provided by HCPs to each yellow fever vaccinee which was amended in line with the revisions of the most recent SmPC (dated 15 Feb 2021).

The MAH is also asked to evaluate the effectiveness of implementation of the UK checklist and PIL. Therefore, this post-authorisation safety study (PASS) survey is designed to assess the effectiveness of the UK (STAMARIL®) yellow fever pre-vaccination checklist among the qualified HCPs of designated authorised YFVCs. In addition, this survey will also assess the effectiveness of the the STAMARIL® PIL among yellow fever vaccinees (or their parents/guardians if vaccinees are younger than 18 years old) in the UK.

31-May-2023 Version number: 3.0

Research question and objectives:

The aim of the current study is to examine the effectiveness of the UK (STAMARIL®) yellow fever pre-vaccination checklist among qualified HCPs of designated authorised YFVCs and of the STAMARIL® PIL among yellow fever vaccinees in the UK, by conducting a survey in this population.

The primary objectives of this study are:

1. To measure:

- a. Awareness of the UK (STAMARIL®) yellow fever pre-vaccination checklist by qualified HCPs of designated authorised YFVCs in the UK.
- b. Utilisation of any standardised yellow fever pre-vaccination checklist(s) by qualified HCPs of designated authorised YFVCs in the UK.
- c. Distribution of the STAMARIL® PIL by qualified HCPs of designated authorised YFVCs to yellow fever vaccinees in the UK.
- 2. To evaluate knowledge and understanding of the key safety messages associated with yellow fever vaccination in any standardised yellow fever pre-vaccination checklist(s) among qualified HCPs of designated authorised YFVCs in the UK.
- 3. To verify the receipt of the STAMARIL® PIL by yellow fever vaccinees at the time they get vaccination consultation in the UK.

There is no secondary objective. **Study design:**

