8 RESEARCH QUESTION AND OBJECTIVES

The aim of the current study is to examine the effectiveness of the UK (STAMARIL®) yellow fever pre-vaccination checklist among the qualified HCPs of designated authorised YFVCs and of the STAMARIL® PIL among the yellow fever vaccinees in the UK by conducting a survey in this population.

The objectives and endpoints of this study are presented in **Table 1**.

Table 1 Objectives and endpoints

Objectives	Endpoints				
Primary objectives					
To measure: a. Awareness of the UK (STAMARIL®) yellow fever pre-vaccination checklist by qualified HCPs of designated authorised YFVCs in the UK.	a. The proportion of qualified HCPs who are aware of the UK (STAMARIL®) yellow fever pre-vaccination checklist. Success indicator for awareness: if ≥80% of qualified HCPs are successful (a qualified HCP is considered successful when he/she is aware of the UK (STAMARIL®) yellow fever pre-vaccination checklist).				
b. Utilisation of any standardised yellow fever pre-vaccination checklist(s) by qualified HCPs of designated authorised YFVCs in the UK.	 b. The proportion of qualified HCPs who frequently or always use one or both the standardised yellow fever prevaccination checklists. Success indicator for utilisation: if ≥80% of qualified HCPs are successful (a qualified HCP is considered successful when he/she frequently or always uses at least one of the standardised yellow fever pre-vaccination checklists). 				
c. Distribution of the STAMARIL® PIL by qualified HCPs of designated authorised YFVCs to yellow fever vaccinees in the UK.	c. The proportion of HCPs who frequently or always distribute the STAMARIL® PIL to yellow fever vaccinees in the UK. Success indicator for distribution of the STAMARIL® PIL by HCPs: if ≥80% of qualified HCPs are successful (a qualified HCP is considered successful when he/she is frequently or always distributes the STAMARIL® PIL).				

Property of the Sanofi Group - strictly confidential

31-May-2023

Version number: 3.0

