9.4.1 Questionnaire description

The questionnaires have a disclaimer and consent at the beginning. They are designed to collect information on the eligibility and demographics of the participants. The questionnaires include open and closed questions on the contents of the checklist and STAMARIL[®] PIL, and the questions are in the order of exploring knowledge to awareness. The language of both questionnaires (HCPs and vaccinees) will be English.

The questionnaires are designed to be nondirecting, to avoid inducement of social desirability bias, and without any self-evident answers. Also, to avoid information bias, the web questionnaires will be programmed in such a way that the participants cannot go back to the previous questions.

A brief overview of the contents in each of these questionnaires is as below:

HCP questionnaire will include questions on:

- screening criteria, demographics
- awareness of the UK (STAMARIL®) yellow fever pre-vaccination checklist
- utilisation of any standardised yellow fever pre-vaccination checklist(s)
- distribution of the STAMARIL® PIL
- knowledge and understanding of key safety messages

Vaccinee questionnaire will include questions on:

• screening criteria, demographics

• receipt of the STAMARIL® PIL

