questions)	Q7. Please select which of the following standardised yellow fever pre-vaccination checklist(s) you have received or are aware about: Please select all options that apply	Yes	Question completed desirably [Answer: 1 is desirable]	fever pre-vaccination checklist Success for awareness if ≥80% of HCPs are successful.	
	Q8. Please select the option that best describes your experience with the use of the yellow fever pre-vaccination (STAMARIL®) checklist issued by the Medicines and Healthcare products Regulatory Agency (MHRA)	Yes	Question completed desirably [Answers: 1 or 2 are desirable]	An HCP is considered successful for utilization when he/she utilizes either the UK (STAMARIL®) yellow fever pre-vaccination	
Utilization (7 questions)	Q9. Please select the option(s) that best describes why you never/rarely/sometimes use the yellow fever pre-vaccination (STAMARIL®) checklist issued by the Medicines and Healthcare products Regulatory Agency (MHRA): Please select all options that apply	No	Complementary question	yellow fever pre-vaccination checklist or traveller checklist Success for utilization if ≥80% of HCPs are successful.	

Page 78

Objectives	Questions	Is the question included in the assessment of success? (Yes/No)	Definition of desirably/correctly answered question	Assessment of success
	Q10. Please select the option(s) that best describes the challenges you face while using the yellow fever pre-vaccination (STAMARIL®) checklist issued by the Medicines and Healthcare products Regulatory Agency (MHRA): Please select all options that apply	No	Complementary question	
	Q11.Please select the option that best describes your experience with the use of the yellow fever pre-vaccination checklist (i.e. traveller checklist) issued by the National Travel Health Network and Centre (NaTHNaC) and Public Health Scotland (PHS)	No	Question completed desirably [Answers: 1 or 2 are desirable]	
	Q12. Please select the option(s) that best describes why you never/rarely/sometimes use the yellow fever pre-vaccination checklist (i.e., traveller checklist) issued by the National Travel Health Network and Centre (NaTHNaC) and Public Health Scotland (PHS): Please select all options that apply	No	Complementary question	

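### The HCP invitation explains the survey's objectives before awareness of the UK checklist is asked without a time anchor, so the awareness indicator can be biased upward

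*Protocol*

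**What the plan says.** Under Protocol section 9.2.4.1, HCPs are invited by email and/or phone, and an email invitation carries the link to the questionnaire. The invitation covers the "survey background and objectives, the contact information for questions, and the proposed" "compensation will be explained to the HCPs".

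The objectives name the checklist. Section 8 opens with "The aim of the current study is to examine the effectiveness of the UK (STAMARIL®) yellow fever pre-vaccination checklist", and the first primary objective (section 4, repeated in section 8, Table 1) is "Awareness of the UK (STAMARIL®) yellow fever pre-vaccination checklist by qualified HCPs of designated authorised YFVCs in the UK".

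Inside the questionnaire, section 9.4.1 states that "the questions are in the order of exploring knowledge to awareness", and participants cannot return to earlier questions. Annex 6.1 places five knowledge questions (Q1 to Q5) before two awareness questions. Q6 asks about experience with the standardised checklist(s), with answers 1 or 2 desirable. Q7 reads "Please select which of the following standardised yellow fever pre-vaccination checklist(s) you have received or are aware about", with answer 1 desirable.

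Table 1 sets the indicator at 80% or more of qualified HCPs, where "a qualified HCP is considered successful when he/she is aware of the UK (STAMARIL®) yellow fever pre-vaccination checklist". Section 9.7.1 requires all questions related to awareness to be answered desirably, so both Q6 and Q7 count.

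**The concern.** The indicator is meant to show whether the risk minimisation measure reached HCPs. If the objectives are explained as the protocol words them, every respondent who reads the invitation has met the name of the UK checklist before Q6 and Q7. Q7 then asks what the HCP is aware of now. Someone who learned of the checklist from the invitation can tick it truthfully.

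The protocol recognises this kind of leakage within the form: it orders knowledge before awareness and blocks backward navigation. Those controls cannot act on a message read before the form is opened. Carry-over from the invitation can only raise the awareness proportion. The collected data could not separate awareness due to the measure from awareness due to the survey, and weighting by region would not remove the difference.

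**Working it through.** **Sequence of events, from the text**

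1. The invitation explains the objectives (9.2.4.1).
2. The aim and objective 1a name the UK checklist (sections 4 and 8).
3. The HCP opens the link and answers Q1 to Q5, then Q6 and Q7 (9.4.1, Annex 6.1).
4. Neither Q6 nor Q7, as shown in Annex 6.1, is tied to the time before the invitation.
5. Section 9.9.2 covers selection bias, recall bias and social desirability bias. For HCPs' recall of having received the measures it names only underestimation. Disclosure through the invitation is not mentioned.

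Q6 concerns the standardised checklist(s) in general. Section 7 reports that more than 90% of centres in England, Wales and Northern Ireland used a traveller checklist in 2020. An HCP might therefore answer Q6 desirably from experience with that checklist alone. The answer options are not shown, so this remains a possibility.

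**The plan's own precision figure**

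Section 9.5.1 uses n = P(1−P)z²/e². With P = 0.50, z = 1.96 and e = 0.07, n = 0.25 × 3.8416 / 0.0049 = 195.99, matching the 196 in Table 2. At the minimum of 200 HCPs the half-width is 1.96 × √(0.25/200) = 6.93 percentage points. This describes sampling error only; a systematic shift comes on top of it.

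**Illustration of the shift (p and f are assumptions; the protocol gives neither)**

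Let p be the proportion who would be scored aware without the invitation. Let f be the share of the remaining respondents who are scored aware on both Q6 and Q7 because of it. Expected observed awareness is p + f(1−p). It reaches 80% at f = (0.80−p)/(1−p):

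- p = 0.50: 0.30/0.50 = 60%
- p = 0.60: 0.20/0.40 = 50%
- p = 0.70: 0.10/0.30 = 33%
- p = 0.75: 0.05/0.25 = 20%

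Taking the 80% rule as applying to the observed unweighted proportion, and treating 200 respondents as independent, the binomial chance of at least 160 successes is:

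| Assumed p | f = 0 | f = 0.10 | f = 0.25 | f = 0.50 |
|---|---|---|---|---|
| 60% | <0.1% | <0.1% | 0.1% | 54.2% |
| 70% | 0.1% | 1.4% | 22.5% | 97.8% |
| 75% | 5.8% | 22.5% | 71.1% | 99.9% |

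If p is already 80% or more, the expected proportion meets the threshold without any carry-over.

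**The case against.** The strongest reply is that the protocol does not say the invitation names the checklist. It says that the objectives are explained, and the invitation text is not in the document. Section 9.2.4.1 itself paraphrases the objective as awareness and knowledge of the safety information in the measures, and the study title refers only to local risk minimisation measures. An invitation in those terms would comply and leak little. This stands: the protocol permits the bias but does not establish that it occurs.

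Second, success needs Q6 as well as Q7, and whether an HCP who saw only the invitation could truthfully pass Q6 cannot be judged without the answer options. This also stands and limits the size of the effect.

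Third, section 10 says participants will be informed of the purpose of the investigation. That does not require naming the checklist before Q6 and Q7; a general purpose statement, with full objectives afterwards, is compatible with it.

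Fourth, data collection began in March 2023, so a change now falls within fieldwork. This is a real cost. Under section 6, however, collection runs to August-September 2023, so later respondents can still benefit.

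A reader might also infer three further points that the text does not support:

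- **Reminders make it worse.** The protocol does not say that reminders repeat the objectives.
- **The invitation contradicts section 9.4.1.** The statement there, "The questionnaires are designed to be nondirecting, to avoid inducement of social desirability bias, and without any self-evident answers", is about the questionnaires, not the invitation.
- **Use and leaflet distribution are inflated by the same route.** Q8, Q11 and Q15 score frequent or constant practice, and reading an invitation cannot create such a history. Social desirability in those answers is a separate matter, already discussed in general terms in section 9.9.2.

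**Conclusion.** The point holds as a possible, unacknowledged upward bias on one primary indicator, awareness of the UK checklist. It rests on the invitation explaining the objectives in a form that names the checklist, and on some previously unaware HCPs then answering both Q6 and Q7 desirably. The protocol rules out neither.

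A reader might go further and conclude that the design creates the awareness it sets out to measure. The documents do not support that: only HCPs unaware beforehand can be affected, and the invitation wording and answer options are not available. The size is unknown. The illustration shows only that carry-over of 20% to 50% among the unaware would lift prior awareness of 75% down to 60% to the threshold in expectation. No value in that range is established. The sample size calculation is not affected.

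**What to change.** - **Section 9.2.4.1:** state that the invitation and phone script describe the purpose in general terms, for example yellow fever vaccination practice and safety information, without naming the UK checklist. Give the full objectives after submission. Check that the disclaimer and consent text at the start of the questionnaire is worded the same way.
- **Q6 and Q7 only:** add a stem such as 'Before you were invited to this survey, ...'.
- **Section 9.9.2:** for HCPs already surveyed, state the possible upward bias in awareness.
- **Reporting:** show awareness separately before and after the wording change. Completion date and time are already recorded under 9.2.4.1. HCPs invited under the existing wording who complete the revised items should be identified as such.

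The cost is rewording the invitation, the phone script and two question stems, plus a new version of the HCP questionnaire, which Annex 1 dates 10 October 2022. The downside is two versions of a primary-endpoint item within one fieldwork period, with fewer respondents in each. If few HCPs remain to be surveyed, the limitation statement will carry most of the benefit.
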